8.2.2 Relationship to Study Agent

We will apply NCI-CTCAE criteria for attribution of AE by means of the following descriptors and codes, following the NCI guidelines for their application.

1

5

- unrelated to treatment
- unlikely related to treatment 2
- possibly related to treatment 3
- probably related to treatment 4
- definitely related to treatment

8.2.3 Expectedness

Expectedness of AEs will be evaluated based on clinical phase I and Phase II studies (see Section 2.1.7; Clinical Experience). Unexpectedness will be defined as any AE occurring in one or more subjects where the nature, severity, or frequency of which is **not** consistent with either:

- 1. the known or foreseeable risk of adverse events associated with the procedures involved in the research that are described in (a) the IRB-approved research protocol, (b) investigator brochure, (c) IRB-approved informed consent document; or
- 2. the expected natural progression of the underlying disease or condition of the subject(s) and the subject's predisposing risk factor profile for the adverse event.

8.3 Time Period and Frequency for Event Assessment and Follow-Up

All AEs occurring from screening (V1) until the time of the follow-up phone call 8 weeks after study drug administration will be recorded on the Adverse Event form in the subject's CRF, irrespective of severity or whether or not they are considered medication-related. Onset of chronic illness (e.g. autoimmune disorders, asthma, type 1 diabetes and allergies) and conditions prompting emergency room (ER) visits or physician office visits that are not related to well-child care, injury, or common acute illnesses (e.g., upper respiratory tract infection, otitis media, pharyngitis, and gastroenteritis) will be reported during the entire study period. The investigator will inquire about the occurrence of AEs at every visit/contact during the study and throughout the follow-up phase as appropriate. All AEs either observed by the investigator or a clinical collaborator or reported by the subject's parent/guardian spontaneously or in response to a direct question will be evaluated by the investigator. AEs not previously documented in the study will be recorded in the Adverse Event form within the subject's CRF. The nature of each event, date and time (where appropriate) of onset, outcome, intensity and relationship to drug administration should be established. Details of any corrective treatment should be recorded on the appropriate page of the CRF.

8.4 Reporting Procedures

8.4.1 Adverse Event Reporting

When an AE/SAE occurs, it will be the responsibility of the investigator to review all documentation (e.g., hospital progress notes, laboratory, and diagnostic reports) relative to the event. The investigator will then record all relevant information regarding an AE/SAE on the eCRF or SAE Report Form as applicable. The investigator will attempt to establish a diagnosis of the event based on signs, symptoms, and/or other clinical information.

8.4.2 Serious Adverse Event Reporting

All safety data will be reported to the PI/Sponsor, DSMB, IRB, and FDA every six months, or, in the case of any major safety concern or question, immediately. All SAEs will be reported to the PI/Sponsor within 72 hours. If any study stopping condition occurs, this will be reported immediately, and the study will be halted, pending review by these agencies. The investigator has a legal responsibility to promptly notify, as appropriate, both the local regulatory authority and other regulatory agencies about the safety of a product under clinical investigation. Prompt notification of SAEs by the investigator to the Study Contact for Reporting SAEs is essential so that legal obligations and ethical responsibilities towards safety of other subjects are met. The investigator, or responsible person according to local requirements, will comply with the applicable local regulatory requirements related to the reporting of SAEs to regulatory authorities and the IRB. This protocol will be filed under an Investigational New Drug (IND) status with the US FDA. A given SAE may qualify as an IND Safety Report if the SAE is both attributable to the investigational product and unexpected. In this case, all investigators filed to the IND (and associated INDs for the same compound) will receive an Expedited Investigator Safety Report (EISR), identical in content to the IND Safety Report submitted to the FDA.

An EISR is required for: a) development compounds (i.e. compounds not marketed), if the event is serious, unexpected and has a suspected relationship to study drug treatment. Expected adverse events for development compounds will be described; b) marketed compounds (i.e. approved in a least one market), if the event is serious, unexpected and has a suspected relationship to treatment with a drug product AND is a significant new emerging safety issue. Expected adverse events for marketed compounds will be described in the Core Safety Information (CSI). An EISR is required if an SAE was expedited to the IND in the US or to fulfill regulatory obligations in other countries. The purpose of the EISR is to fulfill specific regulatory and Good Clinical Practice (GCP) requirements, regarding the product under investigation.

8.4.3 Unanticipated Problem Reporting

All unanticipated problems will be reported to the drug manufacturer, PI/Sponsor, DSMB, IRB, and FDA every six months, or immediately in the case of any major safety concern or question. Unanticipated problems that are serious adverse events will be reported to the IRB within 1 week of the investigator becoming aware of the event. Unanticipated problems will be defined as any incident, experience, or outcome that meets **all** of the following criteria:

- unexpected (in terms of nature, severity, or frequency) given (a) the research procedures that are described in the protocol-related documents, such as the IRB-approved research protocol and informed consent document; and (b) the characteristics of the subject population being studied;
- related or possibly related to participation in the research (in this guidance document, *possibly related* means there is a reasonable possibility that the incident, experience, or outcome may have been caused by the procedures involved in the research); and
- suggests that the research places subjects or others at a greater risk of harm (including physical, psychological, economic, or social harm) than was previously known or recognized

8.4.4 Events of Special Interest

An AE of special interest (serious or non-serious) is defined as one of scientific and medical concern specific to the AMO-01 for which ongoing monitoring and rapid communication by the investigator to the sponsor is appropriate. Such an event might warrant further investigation in order to characterize and understand it. Depending on the nature of the event, rapid communication by the investigator to the IRB, DSMB, and FDA might also be warranted. A report of events of special interest will be generated and include AEs of special interest that are unexpected as defined (see section 8.2.3). An example that may be relevant to AMO-01 would

be an anaphylactic reaction which has been reported in one patient previously when the intravenous catheter was flushed too quickly.

8.4.5 Reporting of Pregnancy

If serum pregnancy results are positive, the lead investigator will inform the subject and the caregiver with the subject's consent and it will be documented in the case report form.

8.5 Study Halting Rules

As indicated in the Synopsis, the following criteria will be used to identify possible adverse treatment events, which will indicate the need to halt active participation of the subject in the study:

- Withdrawal of Consent
- PI or any regulatory authority (DSMB, IRB, or FDA) believe withdrawal is necessary for the subject's health, well-being, or best interests.
- PI or any regulatory authority believe that withdrawal is necessary for the subject's health, well-being, or best interests
- Laboratory: any abnormality on any test with adverse event (AE, Common Terminology Criteria for Adverse Events, National Cancer Institute, scales) ≥ 3 or greater at any time in the study
- Any AE of any sort (clinical, laboratory) \geq 4 will result in halting for the individual and also for the study as a whole.

To avoid bias, all analyses will include all subjects, including those withdrawn from the study, regardless of adherence to study protocol. Especially in a phase I/II of exploratory trial of a novel, unproven treatment, the safety of subjects must be the primary *overriding* concern. If there is doubt concerning a subject's safety, the default mode must be withdrawal from treatment or active study participation, followed by close observation (safety follow up visits) and recommendation of standard treatment.

If a subject is withdrawn from active study during screening or observation phases of the study, they will be returned to the referring physician and standard care will be recommended; in addition we will request the subject's participation in an end-of-study visit, as per the schedule of the part of the study.

If a subject is withdrawn from active study during treatment, they will also be returned to the referring physician and standard care will be recommended; however, in this case, we will in addition request the subject's participation in clinical and laboratory safety assessments and follow up per protocol schedule.

Stopping Conditions for Study as a Whole

The study will be halted* if two patients experience stopping conditions across sites. Any patient experiencing stopping conditions will be reported to the PI/Sponsor immediately (Exceptions for this criterion: Patients who withdraw voluntarily for reasons not directly related to or intrinsic to the study, e.g. incidental considerations such as concerns about travel time to study visits, unexpected pregnancy in the family, etc.). In addition, the study will be halted if one patient experiences a serious related adverse effect (grade \geq 4 AE).

All safety data will be reported to the PI/Sponsor, DSMB, IRB, and FDA every six months, or, in the case of any major safety concern or question, immediately. If any study stopping condition occurs, this will be reported immediately and the study halted, pending review by DSMB, IRB, and FDA, and until the decision by regulatory authorities to resume, suspend or close the study has been made.

*Operationally, "halting" will ordinarily mean that no further screening of new subjects and no treatment initiation will occur until the safety issue has been investigated and resolved (i.e., a final decision has been made to resume, suspend or close the study has been made). Enrolled study participants who have no new symptoms or adverse effects will ordinarily be allowed to continue study observation or treatment without interruption while the safety issue is being investigated, unless it is the contemporaneous judgment of the PI or

subsequent judgment of the DSMB, IRB, or FDA that it is unsafe to do so, in which case all observation or treatment interventions will be suspended forthwith.

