5.5 Premature Termination or Suspension of Study

The following criteria will be used to identify possible adverse treatment events, which will indicate the need to halt active participation of the subject:

- Withdrawal of Consent
- PI or any regulatory authority (Safety Monitoring Board, IRB) believe withdrawal is necessary for the subject's health, well-being, or best interests.
- Any serious related AE of any sort (clinical, laboratory) \geq 4 will result in halting for the individual and also for the study as a whole.

Return of a subject to active study participation will not be permitted, except if a transient clinical or laboratory abnormality unrelated to study treatment has occurred and subsequent permission of the Safety Monitoring Board to return the patient to active study has been provided.

If a subject is withdrawn from active study during screening or observation phases of the study, they will be returned to the referring physician and standard care will be recommended; in addition we will request the subject's participation in an end-of-study visit

If a subject is withdrawn from active study during treatment, they will also be returned to the referring physician and standard care will be recommended; however, in this case, we will request the subject's participation in clinical and laboratory safety assessments and follow up per protocol schedule.

The study will be halted* if two patients experience stopping conditions across sites. (Exceptions for this criterion: Patients who withdraw voluntarily for reasons not directly related to or intrinsic to the study, e.g. incidental considerations such as concerns about travel time to study visits, unexpected pregnancy in the family, etc. In addition, the study will be halted if one patient experiences a serious related adverse effect (grade \geq 4 AE).

All safety data will be reported to the Safety Monitoring Board and IRB every six months, or, in the case of any major safety concern or question, immediately. If any study stopping condition occurs, this will be reported immediately and the study halted, pending review by the Safety Monitoring Board and IRB, and until the decision by regulatory authorities to resume, suspend or close the study has been made.

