*Operationally, "halting" will ordinarily mean that no further screening of new subjects and no treatment initiation will occur until the safety issue has been investigated and resolved (i.e., a final decision has been made to resume, suspend or close the study has been made). Enrolled study participants who have no new symptoms or adverse effects will ordinarily be allowed to continue study observation or treatment without interruption while the safety issue is being investigated, unless it is the contemporaneous judgment of the PI or subsequent judgment of the Safety Monitoring Board or IRB that it is unsafe to do so, in which case all observation or treatment interventions will be suspended forthwith.

6 Study Agent and Administration

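### Sections 5.5 and 8.5 give conflicting triggers for halting the study, 8.5 also conflicts with itself, and nothing says which wording governs

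*Combined protocol and SAP*

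**What the plan says.** Four statements deal with a single event of grade 4 or above:

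- Section 5.5, third bullet: "Any serious related AE of any sort (clinical, laboratory") of grade ≥ 4 halts the individual and the study.
- Section 5.5, whole-study text: one patient with a serious related grade ≥ 4 event halts the study.
- Section 8.5, last bullet: "Any AE of any sort (clinical, laboratory") of grade ≥ 4 halts the individual and the study. Neither seriousness nor relatedness is required.
- Section 8.5, whole-study text: "In addition, the study will be halted if one patient experiences a serious related adverse effect", again of grade ≥ 4.

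Section 8.5 has a further subject-level condition that is absent from 5.5: "Laboratory: any abnormality on any test with adverse event" grade 3 or above. Both sections carry the same two-patient rule: "The study will be halted* if two patients experience stopping conditions across sites". Both also define halting in the same way: "no further screening of new subjects and no treatment initiation will occur until the safety issue has been investigated and resolved".

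Under Section 8.4.2, a stopping condition is reported immediately, while an SAE goes to the PI/Sponsor within 72 hours. The Synopsis gives two enrolling sites and up to 10 treated subjects.

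**The concern.** A halting rule should work without interpretation. Here the same grade 4 event that is unrelated, or not serious, halts the study under one bullet and not under the other three statements. The two-patient rule has identical words in both sections but counts different events, because only 8.5 lists the laboratory condition. Section 5.5 reads as complete and does not refer to 8.5. A reader of 8.5 alone meets the broad bullet first and the narrow sentence afterwards.

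What is at stake is the next infusion. A site using 5.5 could handle an event as a routine report, with up to 72 hours allowed if it is an SAE, although 8.5 calls for immediate reporting and a pause. Either site could dose another subject in the meantime.

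**Working it through.** **Text comparison**

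| Event | Section 5.5 | 8.5 bullets | 8.5 whole-study text |
|---|---|---|---|
| One serious related AE, grade ≥ 4 | study halts | study halts | study halts |
| One other AE, grade ≥ 4 | no automatic halt | study halts | not named |
| Grade 3 lab, one subject | no automatic condition | subject stopped | counts as one of two |
| Grade 3 labs, two subjects | no automatic halt | both subjects stopped | study halts |

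Consent withdrawal and the judgment of the investigator or board appear in both sections, so they are not part of the difference.

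**Size, for illustration only.** The plan states no halting probability, so there is no figure to reproduce. All rates below are assumptions.

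Inputs per subject:
- p4 = any AE of grade ≥ 4: 5% (low 2%, high 10%)
- s = share of these that are serious and related: 50%
- q3 = grade 3 lab with no grade ≥ 4 AE: 10% (low 5%, high 20%)
- d = share of the remaining events (other grade ≥ 4 AEs and grade 3 labs) for which the investigator withdraws the subject under 5.5: 0, 0.5 or 1
- n = 9, because an event in the tenth subject cannot affect a later infusion

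Let a be the chance that a subject's event halts the study alone, and b the chance that it counts towards the two-patient rule. Then

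P(pause) = 1 − [(1−a−b)^n + n·b·(1−a−b)^(n−1)].

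Base case:
- Wider 8.5 reading, a = 0.05, b = 0.10: 1 − (0.2316 + 0.2452) = 0.523.
- 5.5, d = 0, a = 0.025, b = 0: 1 − 0.975^9 = 0.204.
- 5.5, d = 0.5, a = 0.025, b = 0.5 × (0.025 + 0.10) = 0.0625: 1 − (0.4386 + 0.2704) = 0.291.
- 5.5, d = 1, a = 0.025, b = 0.125: 1 − (0.2316 + 0.3066) = 0.462.

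Every 5.5 pause in this model is also an 8.5 pause, so the chance of disagreement is the difference:

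| Rates | d = 0 | d = 0.5 | d = 1 |
|---|---|---|---|
| Low | 14% | 12% | 5% |
| Base | 32% | 23% | 6% |
| High | 49% | 27% | 3% |

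With s = 25% at base rates the three figures are 42%, 30% and 9%. With s = 75% they are 23%, 17% and 3%.

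**Cost of choosing the wider trigger.** Take n = 10 and one consistent list that keeps the laboratory condition. The chance of a pause is 57% if any grade ≥ 4 AE halts the study. It is 51% if only a serious related one does and other grade ≥ 4 AEs count towards two patients. At low rates the pair is 26% and 20%; at high rates, 89% and 87%.

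**The case against.** The triggers are not exclusive, so a site that applies the widest one breaches nothing. Section 8.5 is the section titled for halting rules, and it says that doubt about a subject's safety is resolved by withdrawal. Section 5.5 keeps investigator and board discretion, the two-patient rule and immediate reporting of major safety concerns. Section 10.4.7 provides ongoing DSMB review. All of this stands and limits the harm. It does not remove the defect, because an automatic trigger is meant not to depend on judgment or on a reader having found both lists.

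The assumed rates may also be too high. Sections 2.1.8.1 and 2.1.8.2 describe laboratory findings in the oncology studies as largely unremarkable, at up to 480 mg/m²/day in 14-day cycles against one 120 mg/m² infusion here, although decreased hemoglobin is among the severe events. Clinically significant laboratory abnormalities at screening are excluded. The figures should therefore be read only as a scale.

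Three stronger readings are tempting, and the documents do not support them.

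- *Different bodies review a halt.* Section 5.5 has "pending review by the Safety Monitoring Board and IRB" and 8.5 has "pending review by DSMB, IRB, and FDA". The two board names read as one body, 5.5 also waits for a decision by regulatory authorities, and Sections 8.4.2 and 8.6 send safety data to FDA. No harm follows from this difference.
- *The sections disagree in about a third of such trials.* The 32% figure sets discretion under 5.5 to zero, which the text does not justify.
- *The broad bullet is the intended rule.* Three of the four single-event statements require a serious related event, so the bullet is the outlier. The choice belongs to the sponsor and DSMB.

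**Conclusion.** The conflict is real, both between 5.5 and 8.5 and within 8.5, and no text settles it. A site working from 5.5 could miss a pause that 8.5 requires. On the assumed base rates, with half of grade ≥ 4 events serious and related, the chance of such a disagreement among the first nine subjects is about 6% to 32%. The main driver is how often the investigator uses discretion under 5.5. Even these figures overstate the effect on dosing, since some events come after the last infusion.

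Severity is minor to moderate. Only subjects not yet dosed are affected, a halt is a reviewable pause, and no endpoint or analysis changes. The existence of the conflict does not depend on any assumed rate.

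**What to change.** 1. Keep one list, in Section 8.5. Replace the criteria and whole-study sentences in 5.5 with: *Subject-level stopping conditions and whole-study halting rules are those in Section 8.5.*
2. Keep the grade ≥ 3 laboratory condition in 8.5 and state that it counts towards the two-patient halt.
3. Use one identical single-event grade ≥ 4 trigger in the 8.5 bullet and the 8.5 whole-study sentence, chosen by the sponsor and DSMB:
   - *Serious related:* remove the whole-study clause from the bullet, keep the bullet as a subject-level condition, and define related as codes 3 to 5 in Section 8.2.2; or
   - *Any AE:* change the whole-study sentence to match the bullet.

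   Until they decide, apply the wider trigger.
4. In either case, limit study-halting triggers to events after the infusion starts, because AEs are recorded from consent and about 15 subjects will be screened. Exclude the subject's habitual seizures, because every subject has epilepsy and a single unrelated grade 4 seizure could otherwise pause the trial.

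The cost is a wording amendment with DSMB confirmation. It needs no new data, visits or patients. The wider trigger may bring somewhat more pauses: 57% against 51% at the assumed base rates.

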5.4 Participant Withdrawal or termination

5.4.1 Reasons for Withdrawal or Termination

If a subject is discontinued at any time after Baseline (V2), the investigator will make every effort to see the subject and complete the final in-clinic study visit (V6) as soon as possible, ideally within one week of discontinuation of the other scheduled study procedures. A follow-up telephone call will still be attempted 4 weeks later.

Subjects may withdraw from the study at any time without stating a reason and without prejudice to further treatment. The Investigator may withdraw a subject from the study and discontinue study treatment and assessments at any time.

Early discontinuation of any subject who has given informed consent to participate will be recorded including the reason for discontinuation. The primary reason for a subject withdrawing prematurely will be selected from the following standard categories of early discontinuations:

- Failed to meet enrollment criteria.
- Adverse Event: Clinical events occurred or laboratory results are reported that in the medical judgment of the investigator are grounds for discontinuation in the best interests of the subject.
- Withdrawal of Consent: The subject desired to withdraw from further participation in the study. The subject is not obliged to provide any reason for withdrawal of consent, but where a reason is given this will be recorded on the CRF.
- Protocol Violation: The subject failed to adhere to the protocol requirements, at the investigator's discretion
- Lost to Follow-Up: The subject stopped coming for visits and study personnel were unable to contact the subject or caregiver. Every effort should be made to re-contact the subject prior to declaring a subject as lost to follow-up, which must be at least 3 documented attempts. The 3rd must be in writing and confirmed to have been received (e.g. registered post).
- Other: The subject was terminated for a reason other than those listed above, such as termination of study.

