7.1.8 Caregiver-Completed Seizure Diary

A diary will be provided to the subject/caregiver at each visit from Screening (V1) to Week 2 (V5) which should be completed every day. The diary should be returned at each subsequent visit and the diary should be reviewed by a delegated member of the study team. The diary will be collected at Week 4 (V6). The diary should be completed in full so that the following information can be ascertained:

- Date/time of seizure activity
- Length of seizure
- Type of seizure

A copy of the caregiver-completed seizure diary is located in APPENDIX B: Caregiver Completed Seizure Diary.

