7.3.5 Early Termination Visit

In the event of early termination or withdrawal, the subject will complete the assessments scheduled for the final in-clinic study visit (V6). The follow-up phone call will also be attempted. Refer to the schedule of events (Table 1) for a list of assessments to be completed at this visit.

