10.2 Statistical Hypotheses

We hypothesize that the medication will be safe and tolerable as determined by the absence of SAEs and propose that at least 70% of participants enrolled will be able to complete the infusion.

We hypothesize that, when relevant, seizures will be reduced in frequency by at least 25% compared with 'baseline.' More explicitly, the null (H0) and alternative (Ha) hypothesis will be defined as

H0: The average number of weekly seizures at follow-up (week 4) are reduced by less than 25% compared to baseline

Ha: The average number of weekly seizures at follow-up (week 4) are reduced by at least 25% compared to baseline

We hypothesize that EEG abnormalities will be reduced in frequency by at least 25% compared with 'baseline.' More explicitly, the null (H0) and alternative (Ha) hypothesis will be defined as

H0: The average number of EEG abnormalities at follow-up (week 2) are reduced by less than 25% compared to baseline

Ha: The average number of EEG abnormalities at follow-up (week 2) are reduced by at least 25% compared to baseline

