10.4.3 Analysis of the Secondary Endpoint(s)

Seizure frequency will be analyzed on a relative scale, examining the hypothesized percental decrease in number of seizures from baseline to week 4. For this purpose, the log-transformed data will be analyzed and the resulting point estimates and 95% confidence limits from the Wilcoxon signed-rank test will be converted back to the original scale.

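### After a withdrawal between the infusion and Week 4, the plan neither secures Week 4 seizure counts nor says how the subject enters the Week 4 test, although 8.5 puts withdrawn subjects in every analysis

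*Combined protocol and SAP*

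**What the plan says.** - **Who is analysed (8.5).** "To avoid bias, all analyses will include all subjects, including those withdrawn from the study, regardless of adherence to study protocol".
- **What is tested (10.2, 10.4.3).** The null hypothesis reads "H0: The average number of weekly seizures at follow-up (week 4) are reduced by less than 25% compared to baseline", and 10.4.3 adds: "Seizure frequency will be analyzed on a relative scale, examining the hypothesized percental decrease in number of seizures from baseline to week 4". Section 10.4 declares success if the upper 95% limit of the ratio is at or below 0.75.
- **What happens on withdrawal (5.4.1, 7.3.5).** After any discontinuation following V2, the investigator tries to have the subject "complete the final in-clinic study visit (V6) as soon as possible, ideally within one week of discontinuation of the other scheduled study procedures". Section 7.3.5 repeats that the V6 assessments are done at early termination.
- **How long the diary runs (7.1.8).** "A diary will be provided to the subject/caregiver at each visit from Screening (V1) to Week 2 (V5) which should be completed every day". It is collected at V6, and nothing provides for new sheets after that visit.
- **What comes later (5.4.1, 7.1.15).** "A follow-up telephone call will still be attempted 4 weeks later". The call asks whether seizures are the same, worse or better than at Week 4. It collects no counts.
- **Missing data (10.4.5).** No major problem is expected and no rule is given.

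**The concern.** The all-subjects rule in 8.5 is there to prevent bias, but it only works if the data exist. For a subject withdrawn in follow-up, the diary normally ends at the early V6, before Week 4. The analyst must then either leave the subject out, which a paired signed-rank test does by default, or substitute an earlier window.

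Loss could be related to outcome. Section 8.5 makes withdrawal the default when a subject's safety is in doubt. Section 8.2.1 removes subjects with neurological signs of grade 3 or higher. The study is open-label. With at most ten subjects, one missing ratio can decide whether the 0.75 rule is met.

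**Working it through.** **1. Timeline of one case.** A grade 3 laboratory value at V4 (Day 7) is a withdrawal criterion in 8.5. Under 5.4.1, V6 ideally follows by about Day 14, and the diary is collected then. Days 15 to 28 are not recorded, and the later call cannot restore them.

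**2. If the subject is dropped.** The plan states no power or error rate for this test, and 10.5 says the sample size has no statistical basis, so there is no figure to reproduce. The inputs are up to 10 treated subjects (4.1), a two-sided 5% level and the 0.75 rule (10.4), and the signed-rank test on logs (10.4.3).

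Let d = log(ratio/0.75) and let T+ be the rank sum of the positive d. The upper limit is at or below 0.75 exactly when T+ ≤ k, where k is the largest value with P(T+ ≤ k) ≤ 0.025. This gives k = 8 for n = 10, k = 5 for n = 9 and k = 3 for n = 8. At a true ratio of 0.75 with symmetric log-ratios, all 2^10 = 1024 sign patterns are equally likely. The enumerated results hold for any SD or symmetric shape.

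| Week 4 data | Rule met |
|---|---|
| All ten | 25/1024 = 2.4% |
| One lost, unrelated to outcome | 10/512 = 1.95% |
| One lost, correlated 0.5 with the log-ratio | about 3.6% |
| One lost at random from the worst three | about 4.0% |
| The single worst lost | 74/1024 = 7.2% |
| The worst two lost | 169/1024 = 16.5% |

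The correlated row is simulated: withdrawal score = 0.5·z + √0.75·noise, with z the standardised log-ratio (normal), and the highest score is lost. 100,000 trials gave 3.6%; a repeat with 1,000,000 gave 3.5%. The worst-three row is also simulated under normality.

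Away from the boundary the rates are lower. With a true ratio of 0.85 and an assumed log-SD of 0.4 to 1.0, the rule is met in 0.2–1.0% with all ten and 1.0–3.5% with the worst lost. With a true ratio of 1.0 and the same SDs, it is met in at most 1.1% with the worst lost.

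**3. One subject can change the answer (assumed ratios).** Take nine subjects at 0.45, 0.5, 0.55, 0.6, 0.6, 0.6, 0.65, 0.7 and 0.7, and a tenth at 1.5. The upper limit with the tenth counted is the 9th largest of 55 Walsh averages, 0.87, so the rule is not met. With the tenth dropped it is the 6th largest of 45, 0.65, so the rule is met.

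**4. If the partial diary is used instead.** Suppose seizures halve for 5 days and then return to baseline. Five days is the persistence reported in the mouse (2.1.4); the halving is an assumption. Over d days the ratio is (5 × 0.5 + (d − 5))/d:

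- d = 7: 4.5/7 = 0.64
- d = 14: 11.5/14 = 0.82
- d = 28: 25.5/28 = 0.91

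The same course of seizures falls below 0.75 if the diary stops at Day 7 and well above it at Day 28.

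**5. How often this could arise.** The documents give no dropout rate. At an assumed 5% or 10% risk per subject, the chance of at least one withdrawal in ten is 1 − 0.95^10 = 40% or 1 − 0.90^10 = 65%.

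**The case against.** A reader might infer that the Week 4 test cannot include withdrawn subjects at all, so that the sections contradict each other. The documents do not support that.

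- Section 10.4 equates week 4 with follow-up 4, which is V6 in Table 1, so an early V6 could be entered as the subject's value.
- The weekly average in 10.2 has no defined window, so a rate from a partial diary could serve.
- For withdrawal during treatment, 5.4.2, 5.5 and 8.5 request follow-up on the protocol schedule.
- Section 10.1 defers analysis details to a separate SAP, which may contain a mapping rule.

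All of this stands, but it leaves a gap. The scheduled follow-up is worded around safety assessments and applies to withdrawal during treatment, here a 6-hour infusion. Withdrawals in the observation phase are asked only for an end-of-study visit. An early V6 gives a value, but for a different period (step 4). A SAP can choose a rule; it cannot recover diary days that were never collected.

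It is also fair that withdrawal may be rare after a single infusion, and that a laboratory withdrawal need not relate to seizures. Eligibility sets no minimum seizure count, so zero counts may leave fewer than ten usable log-ratios even without withdrawals. This is one secondary endpoint of an exploratory study.

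**Conclusion.** The point holds as a minor one: the plan does not secure Week 4 seizure counts after a post-infusion withdrawal and does not say how such a subject enters the 25% test, so the all-subjects intention in 8.5 is not backed by data collection.

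A reader might take 7.2% as the trial's false-pass rate. It is not. It requires a true reduction of exactly 25%, ten usable and symmetric log-ratios, exactly one loss, and that loss being the worst ratio. A loss correlated 0.5 with outcome gives about 3.6%, and an unrelated loss about 2%, which is no inflation. The direction of the bias under outcome-related loss is clear; its size in this trial is unknown, because neither the number nor the cause of withdrawals can be known from the documents. Where consent is withdrawn, the data end in any case.

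**What to change.** **Data collection (5.4.1, 5.4.2, 7.3.5, 8.5).** For every post-infusion withdrawal, ask the caregiver to keep the diary to Day 28 unless consent is withdrawn. Review the diary and hand out further sheets at the early V6. Collect them by mail, or take the counts at the call already planned 4 weeks later.

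**Analysis (10.4.3).** Use those counts in the 25% analysis. If a diary still stops early, use the weekly rate over the available post-infusion days. List each such subject with the last diary day and any change in antiseizure or rescue medication, and report the 0.75 rule with and without these subjects.

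**Cost.** A few sentences, with no new visit or form. Caregivers keep the diary for up to about four more weeks, and some will decline. Some counts after withdrawal may reflect other care, which the all-subjects rule in 8.5 already accepts.

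**Effect on the chance of success** (assumed median ratio 0.5, log-SD 0.6). Keeping a tenth count that would have been lost at random raises the chance of meeting the rule from 37% to 46%. If the worst subject would have been dropped, the chance falls from 66% to 46%, which is the removal of the bias.
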